6.3 Treatment Period

Transarterial Radioembolization (TARE) treatment visit (Day 1-31)

- A brief abdominal ultrasound (without contrast) will also be performed prior to radioembolization to ensure the target lesion is visible on ultrasound.
- Post treatment CEUS exams with microbubble cavitation 1-4 hours after TARE

Post-TARE visit 1 (Day 8-38)

- Post treatment CEUS exams with microbubble cavitation approximately 1 week after TARE

Post-TARE visit 2 (Day 15-45)

- Post treatment CEUS exams with microbubble cavitation approximately 2 weeks after TARE

6.4 Long Term/Survival Follow-up

After the subjects have completed treatment, they will be followed through the EMR system to for up to 1 year document long term outcomes.

6.5 Withdrawal Visit/Discontinuation of Therapy

Patients who withdraw or are withdrawn from the study, will stop further CEUS procedures, as described by the study protocol. The reason for discontinuation shall be recorded. The investigators will follow any patient who develops significant adverse events.

Patients may be discontinued from study treatment and assessments at any time. Specific reasons for discontinuing a patient for this study are:

- Voluntary discontinuation by the patient who is at any time free to discontinue his/her participation in the study, without prejudice to further SoC treatment.
- Patient lost to follow-up.
- Safety reason as judged by the Principal Investigators.
- Severe non-compliance to protocol as judged by the Principal Investigators.
- Incorrect enrolment i.e., the patient does not meet the required inclusion/exclusion criteria for the study.
- Disease progression and/or rapidly deteriorating ECOG performance status.
- Deterioration in the patient's condition which in the opinion of the Principal Investigator warrants UTMD discontinuation (to be recorded as an AE or under Investigator Discretion)
 - Patient requires dialysis at any visit
 - Deteriorating liver function
- Related Serious Adverse Event
- A female patient becoming pregnant
- Any reason why, in the opinion of the investigator, the patient should not participate

The whole trial may be discontinued at the discretion of the PI or the sponsor in the event of any of the following:

- Occurrence of AEs unknown to date in respect of their nature, severity and duration
- Medical or ethical reasons affecting the continued performance of the trial

The sponsor and principal investigator will promptly inform all investigators and the relevant regulatory authorities of the termination of the trial along with the reasons for such action

7 Study Procedures and Evaluations

7.1 Study Procedures/Evaluations

- Medical history will be obtained from the electronic medical records (EMR) system and during the first study visit < 1 month before the TARE.
- Volumetric CEUS exam will be obtained approximately < 1 month before the treatment as described in section 5.8.
- Three CEUS exam with microbubble cavitation will be performed 2-4 hours, 1 week, and 2 weeks after treatment as described in section 5.8.

8 Evaluation of Safety

8.1 Specification of Safety Parameters

8.1.1 Unanticipated Problems

Unanticipated problems (UAPs) include, in general, any incident, experience, or outcome that meets the following criteria:

- Unexpected in terms of nature, severity, or frequency given (a) the research procedures that are described in the protocol-related documents, such as the IRB-approved research protocol and informed consent document; and (b) the characteristics of the participant population being studied;

UAPs are considered to pose risk to participants or others when they suggest that the research places participants or others at a greater risk of harm (including physical, psychological, economic, or social harm) than was previously known or recognized.

8.1.2 Adverse Events

An AE is any untoward or unfavorable medical occurrence in a human participant, including any abnormal sign (for example, abnormal physical exam or laboratory finding), symptom, or disease, temporally associated with the participant's participation in the research, whether or not considered related to the participant's participation in the research. All AEs, including observed or volunteered problems, complaints, signs or symptoms, and diagnoses, occurring from the study treatment will be recorded on a serious or non-serious AE data form. Whenever possible, the AE will be evaluated and reported as a diagnosis rather than individual signs and symptoms. If a definitive diagnosis is not possible, the individual signs and symptoms will be recorded. The investigator will evaluate and note the duration, intensity, and relationship to (association with) the treatment or imaging procedures, the action taken, and the determination of seriousness for each AE. The intensity of the AE will be characterized as mild, moderate, or severe.

Optison is well tolerated and has been used extensively in echocardiography applications. In pre-market clinical trials, Optison was administered to 279 patients. In these patients 47 (16.8%) reported at least one adverse event. Of these events, 1 was classified as serious and required antihistamines for hypersensitivity manifestations of dizziness, nausea, flushing, and temperature elevation. No deaths were reported. All of the non-serious reported side effects have been transient, usually lasting only a few minutes. Please see table 1 and the attached Optison Product insert (Appendix B).

8.1.3 Serious Adverse Events

A serious adverse event (SAE) is one that meets one or more of the following criteria:

- Results in death
- Is life-threatening (places the participant at immediate risk of death from the event as it occurred)
- Is disabling or incapacitating

- Results in inpatient hospitalization or prolongation of existing hospitalization
- Results in a persistent or significant disability or incapacity
- Results in a congenital anomaly or birth defect
- An important medical event that may not result in death, be life threatening, or require hospitalization may be considered an SAE when, based upon appropriate medical judgment, the event may jeopardize the participant or may require intervention to prevent one of the outcomes listed in this definition.

8.2 Safety Assessment and Follow-Up

The PI will follow adverse events with start dates occurring any time after informed consent is obtained until 7 (for non-serious AEs) or 30 days (for SAEs) after the last day of study participation. At each study visit, the investigator (or designee) will inquire about the occurrence of AE/SAEs since the last visit. Events will be followed for outcome information until resolution or stabilization.

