3.4 Duration of Follow Up

After the subjects have completed treatment, they will be followed through the electronic medical record (EMR) system for up to 1 year to document long term outcomes.

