11.1 Study Hypotheses

H1: Contrast reperfusion time, degree of tumor enhancement relative to the surrounding parenchyma, tumoral IFP and 3D morphological features of the vasculature quantified via CEUS before therapy correlate with SoC mRECIST reads of non-HCC tumor patients treated with TARE.

H2: mRECIST reads for non-HCC tumor patients receiving TARE combined with microbubble inertial cavitation have more complete response (CR) and partial response (PR) reads compared to the historical group treated with TARE alone.

H3: Patient's time to required next treatment and overall survival are longer for non-HCC tumor patients receiving TARE combined with microbubble inertial cavitation compared to the historical group treated with TARE alone.

H4: Observed and self-reported adverse events, and changes in liver function tests (LFTs) one month post-TARE in non-HCC tumor patients receiving TARE combined with microbubble inertial cavitation are similar compared to the historical group treated with TARE alone.

H5: Values of tumor perfusion and residual vascularity quantified by CEUS 2-4 hours, 1 week, and 2 weeks after TARE therapy are lower in CR and PR mRECIST reads of non-HCC tumor patients treated with TARE.

H6: Reductions of tumor perfusion and residual vascularity values quantified by CEUS 2-4 hours, 1 week, and 2 weeks after TARE therapy are more frequent in CR and PR mRECIST reads of non-HCC tumor patients treated with TARE.

H7: Tumoral response in mRECIST reads of MRI or CT (obtained clinically from patients treated with TARE) at 1 month post treatment will agree with response in their mRECIST reads at 3-6 months.

H8: Values of IFP quantified by SHAPE 2-4 hours, 1 week, and 2 weeks after TARE therapy are lower in CR and PR mRECIST reads of patients treated with TARE.

H9: Reductions of IFP values quantified by SHAPE 2-4 hours, 1 week, and 2 weeks after TARE therapy are more frequent in CR and PR mRECIST reads of patients treated with TARE.

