11.3.1 Safety Review

Safety outcomes will be compared between the treatment group and the historical group using observed and self-reported adverse events, and changes in LFTs one month post-embolization (performed as part of clinical standard of care). LFTs will include blood tests for alanine aminotransferase, alkaline phosphatase, aspartate aminotransferase, bilirubin, albumin, total protein, and prothrombin time. SPECT imaging will be evaluated for all patients by two blinded radiologists to evaluate if the initial UTMD session skews microsphere distribution in the liver.

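### The adverse-event part of H4 sets prospectively solicited events in enrolled patients beside control events with no stated window, source or grading

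*Combined protocol and SAP*

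**What the plan says.** **Enrolled patients.** Section 8.2 starts collection at informed consent and runs it "until 7 (for non-serious AEs) or 30 days (for SAEs) after the last day of study participation". The method is active: "At each study visit, the investigator (or designee) will inquire about the occurrence of AE/SAEs since the last visit". Sections 8.3 and 8.3.3 require onset and end dates, causality and a CTCAE version 5.0 grade. Under section 6.3 the last study procedure is the third UTMD session: "Post treatment CEUS exams with microbubble cavitation approximately 2 weeks after TARE". Section 3.4 adds that patients are "followed through the electronic medical record (EMR) system for up to 1 year to document long term outcomes".

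**Historical controls.** Section 11.2 takes 20 controls from recently treated patients at the same institution and matches them by propensity score. It does not say over what period their adverse events are read, from what source, or how they are graded.

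**The comparison.** H4 in section 11.1 expects "Observed and self-reported adverse events, and changes in liver function tests (LFTs) one month post-TARE" to be similar in the two groups. Section 11.3.1 repeats it: "Safety outcomes will be compared between the treatment group and the historical group using observed and self-reported adverse events". Section 11.2 makes H4 descriptive, with no hypothesis test, and no criterion for similarity is given.

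**The concern.** With no test and no margin, the side-by-side counts are all the evidence that the adverse-event part of H4 will offer. Those counts depend on how long each patient is observed and on whether anyone asks. For enrolled patients both are set in the protocol. For controls neither is, and patients treated in the past had no consent date and no study visits. A self-reported event in a control exists only if someone wrote it down.

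A difference between the groups, or the absence of one, could thus come from ascertainment alone. Safety of the cavitation procedure is a secondary objective (section 2.1.2) and adverse events are a listed secondary endpoint (section 2.2.1, Secondary). A reader of the results would want to know whether the groups were observed alike.

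There is also a possible mismatch within the plan. Section 8.1.2 counts an abnormal laboratory finding as an adverse event. A non-serious liver-test abnormality first seen at one month would enter the liver-function comparison, yet it could fall outside the adverse-event window of the same patient.

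**Working it through.** H4 has no sample size, power or margin, so there is no planned figure to reproduce. The check is date arithmetic, followed by two illustrations.

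**1. When collection ends in enrolled patients.** Section 6.3 puts TARE on Day 1-31 and the last UTMD visit on Day 15-45, so that visit is 15 − 1 = 45 − 31 = 14 days after TARE. Section 8.2 does not define the last day of participation, so both readings are shown.

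| Last day of participation | Non-serious events end | SAEs end |
|---|---|---|
| 2-week UTMD visit | 14 + 7 = day 21 after TARE | 14 + 30 = day 44 after TARE |
| End of record follow-up (up to 1 year) | about 1 year + 7 days | about 1 year + 30 days |

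The first reading is the more natural. The Study Summary gives participation as 3-6 weeks, and section 3.4 starts record follow-up after treatment is complete. Appendix A lists nominal visit days 7, 14 and 21 with wide tolerances and no stated anchor, so the section 6.3 schedule was used. A visit one day early or late moves day 21 to day 20 or 22.

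**2. When collection starts.** Study entry is Day 0 and TARE may be as late as Day 31, so up to 31 pre-TARE days count. They include the pre-treatment Optison infusion. Controls have no counterpart.

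**3. Coverage of one month after TARE, first reading.** Non-serious events: 21/30 = 70% of days, leaving 9/30 = 30% uncovered. SAEs: fully covered, since 44 > 30. These are shares of days, not of events. The 30-day horizon is an assumption, because the plan ties the time point clearly only to "changes in liver function tests (LFTs) one month post-TARE".

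**4. Effect of window length alone (illustration).** Assume a constant hazard and a 30-day risk p of a non-serious event. The risk over W days is 1 − (1 − p)^(W/30). The control window is not in the documents; 30 to 90 days is an assumed range.

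| 30-day risk p | Enrolled, 21 days | Identical controls, 30 days | Identical controls, 90 days |
|---|---|---|---|
| 20% | 14.5% | 20% | 48.8% |
| 40% | 30.1% | 40% | 78.4% |
| 60% | 47.3% | 60% | 93.6% |

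If controls were also read over 21 days, this effect would be zero.

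**5. The opposing effect.** Active inquiry and pre-TARE events raise the enrolled count. The documents do not say how many events charts miss. Take p = 40%, complete capture by inquiry over 21 days, and controls read over 30 days. The window effect is cancelled if charts capture 30.1/40 = 75% of affected controls. Above that fraction the enrolled group looks safer, and below it less safe, with no true difference. The sign therefore cannot be settled from the plan.

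**6. Precision in any case.** With 8/20 in each group the Wilson limits are 21.9% and 61.3%. The Newcombe 95% interval for the difference is ±√(0.181² + 0.213²), or ±28 points. With 4/20 in each it is ±25 points.

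**The case against.** The strongest reply is that the plan does not state different windows or sources for the two groups. It states none for controls, and the deflation in step 4 needs controls to be read for longer, which no section says. That is correct: the window defect is an omission. The difference in source is an inference, though a firm one, because patients treated earlier could not have been asked at study visits.

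Second, a reader might infer that non-serious collection certainly stops at day 21, or that 30% of events are lost. Neither is supported. The stop depends on an undefined term, the one-month horizon attaches clearly only to liver tests, and the 30% is calendar time.

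Third, pre-TARE events can be separated with data already planned, since section 8.3 records onset dates. This stands, but the plan does not say that it will be done for H4.

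Fourth, the study is a pilot, H4 is descriptive, and safety is also characterised by vital signs, laboratory tests, examinations and SPECT reads. This limits the consequence. It does not make counts gathered in different ways comparable, and describing them without a test does not remove the bias.

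Finally, enrolled patients have three extra post-TARE examinations with nursing support (section 5.8). These may generate chart entries even when both groups are read from the record, so a common source reduces the imbalance without removing it. That also stands.

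**Conclusion.** The concern holds for the adverse-event part of H4. Followed as written, the plan compares solicited events, counted from up to about a month before TARE, with control events whose window, source and grading are left open and which can in practice only be charted ones. On the natural reading non-serious collection ends about day 21 and SAE collection about day 44; on the other reading collection runs to about one year. The net direction of bias is unknown, so the comparison cannot be called conservative.

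A reader might infer that similarity under H4 cannot be judged at all. The documents do not support that. The liver-function comparison uses standard-of-care tests at one month and is not affected. SAEs are covered past one month on either reading, so for them the problem is source and start date, not an early stop. The point is modest in weight: it concerns a descriptive secondary comparison with wide intervals at 20 per group, and it is cheap to correct.

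**What to change.** - In section 8.2, define the last day of study participation, and record non-serious events in enrolled patients to day 30 after TARE.
- In sections 11.2 and 11.3.1, state that the H4 adverse-event table counts events with onset from TARE to day 30 in both groups, abstracted from the medical record with the same CTCAE grading. Fix these rules before any control chart is read.
- Report solicited, pre-TARE and contrast-related events in enrolled patients in a separate table, without comparison.
- State as a limitation that the extra study visits may still increase charted events in enrolled patients.

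The cost is wording plus chart abstraction for 20 + 20 = 40 patients. The one-month laboratory tests are already standard of care and record follow-up is already planned, so patients have no added visits. The price is that solicited events leave the between-group table, although H4 names self-reported events; its wording should be aligned.

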8.3 Recording Adverse Events

The following subsections detail what information must be documented for each AE occurring during the time period specified in Section 8.2 Safety Assessment and Follow-Up.

If the patient has experienced AE(s), the investigator will record the following information in the AE log:

- The nature of the event(s) will be described by the investigator in precise standard medical terminology (i.e. not necessarily the exact words used by the patient).
- The duration of the event will be described in terms of event onset date and event ended date.
- The intensity of the AE will be described according to Common Terminology Criteria for Adverse Events version 5.0 (CTCAE), for details see National Cancer Institute home page <http://evs.nci.nih.gov/ftp1/CTCAE/About.html> of the AE. The CTCAE displays Grades 1 through 5 with unique clinical descriptions of severity for each AE based on this general guideline:
 - Grade 1: Mild; asymptomatic or mild symptoms; clinical or diagnostic observations only; intervention not indicated.
 - Grade 2: Moderate; minimal, local or noninvasive intervention indicated; limiting age-appropriate instrumental activities of daily living.
 - Grade 3: Severe or medically significant but not immediately life-threatening; hospitalization or prolongation of hospitalization indicated; disabling; limiting self care activities of daily living.
 - Grade 4: Life-threatening consequences; urgent intervention indicated.
 - Grade 5: Death related to AE.
- The Causal relationship of the event to the study medication will be assessed as one of the following:
 - Unrelated: There is not a temporal relationship to investigational product administration (too early, or late, or investigational product not taken), or there is

- a reasonable causal relationship between noninvestigational product, concurrent disease, or circumstance and the AE.
- Unlikely: There is a temporal relationship to investigational product administration, but there is not a reasonable causal relationship between the investigational product and the AE.
- Possible: There is reasonable causal relationship between the investigational product and the AE. Dechallenge information is lacking or unclear.
- Probable: There is a reasonable causal relationship between the investigational product and the AE. The event responds to dechallenge. Rechallenge is not required.
- Definite: There is a reasonable causal relationship between the investigational product and the AE.

- The Expectedness of the AE
- Action taken
- The outcome of the AE – whether the event is resolved or still ongoing.

8.3.1 Relationship to Study Intervention

The relationship to study intervention or study participation must be assessed and documented for all adverse events. Evaluation of relatedness must consider etiologies such as natural history of the underlying disease, concurrent illness, concomitant therapy, study-related procedures, accidents, and other external factors.

The following guidelines are used to assess relationship of an event to study intervention:

1. Related (Possible, Probable, Definite)
 - a. The event is known to occur with the study intervention.
 - b. There is a temporal relationship between the intervention and event onset.
 - c. The event abates when the intervention is discontinued.
 - d. The event reappears upon a re-challenge with the intervention.
2. Not Related (Unlikely, Not Related)
 - a. There is no temporal relationship between the intervention and event onset.
 - b. An alternate etiology has been established.

8.3.2 Expectedness

The PI is responsible for determining whether an AE is expected or unexpected. An AE will be considered unexpected if the nature, severity, or frequency of the event is not consistent with the risk information previously described for the intervention. Risk information to assess expectedness can be obtained from preclinical studies, the investigator's brochure, published medical literature, the protocol, or the informed consent document.

8.3.3 Severity of Event

Adverse events will be graded for severity according to the Common Terminology Criteria for Adverse Events (CTCAE) version 5.0.

8.3.4 Intervention

Any intervention implemented to treat the AE must be documented for all adverse events.

8.4 Safety Reporting

All adverse events and serious adverse events that should be reported as defined in section 8.1.1 will be recorded in the patient's CRF.

All events will be graded by the Investigator according to the CTCAE version 5.0. A grading (severity) scale is provided for each AE term. Every SAE must be documented by the investigator on the SAE pages (to be found as part of the CRF). The SAE Report Form must be completed and signed. SAEs and possible SAEs will be reported to the regulatory authorities as described below. The initial report shall promptly be followed by detailed, written reports if necessary. The initial and follow-up reports shall identify the trial subjects by unique code numbers assigned to the latter.

The sponsor keeps detailed records of all SAEs reported by the investigators and performs an evaluation with respect to causality and expectedness. Based on, among other, SAE reports the sponsor will evaluate whether the risk/benefit ratio associated with study is changed.

We will in all cases follow the ICH Harmonised Guideline Integrated Addendum to ICH E6(R1): Guideline for Good Clinical Practise ICH E6(R2) ICH Consensus Guideline. Link: <https://ichgcp.net/411-safety-reporting/>

